Appendix C.Pregnancy Precautions, Definition for Female of Childbearing
Potential, and Contraceptive Requirements

1) Definitions

a) Definition of Childbearing Potential

For the purposes of this study, a female born subject is considered of childbearing potential following the initiation of puberty (Tanner stage 2) until becoming post-menopausal, unless permanently sterile or with medically documented ovarian failure.

Women are considered to be in a postmenopausal state when they are ≥ 54 years of age with cessation of previously occurring menses for ≥ 12 months without an alternative cause. In addition, women of any age with amenorrhea of ≥ 12 months may also be considered postmenopausal if their follicle stimulating hormone (FSH) level is in the postmenopausal range and they are not using hormonal contraception or hormonal replacement therapy.

Permanent sterilization includes hysterectomy, bilateral oophorectomy, or bilateral salpingectomy in a female subject of any age.

b) Definition of Male Fertility

For the purposes of this study, a male born subject is considered of fertile after the initiation of puberty unless permanently sterile by bilateral orchidectomy or medical documentation.

2) Contraception Requirements for Female Subjects

a) Study Drug Effects on Pregnancy and Hormonal Contraception

No formal studies have been conducted to evaluate the reproductive toxicity of EFX; therefore, the reproductive toxicity of EFX in humans is unknown.

EFX has not yet been studied in pregnant women.

Please refer to the latest version of the Investigator's Brochure for additional information.

b) Contraception Requirements for Female Subjects of Childbearing Potential

The inclusion of female subjects of childbearing potential requires the use of highly effective contraceptive measures. They must have a negative serum pregnancy test at screening and a negative pregnancy test on the Baseline/Day 1 visit prior to enrollment. Pregnancy tests will be performed at monthly intervals thereafter. Female subjects must agree to one of the following from screening until the Week 20 Safety Follow-up Visit.

• Complete abstinence from intercourse of reproductive potential. Abstinence is an acceptable method of contraception only when it is in line with the subject's preferred and usual lifestyle.

Or

- Consistent and correct use of 1 of the following methods of birth control listed below.
 - Intrauterine device (IUD) with a failure rate of < 1% per year
 - Intrauterine hormone-releasing system (IUS) with a failure rate of < 1% per year
 - Tubal sterilization
 - Essure[®] micro-insert system (provided confirmation of success 3 months after procedure)
 - Vasectomy in the male partner (provided that the partner is the sole sexual partner and had confirmation of surgical success 3 months after procedure)

Should female subjects wish to use a hormonally based method, use of a male condom by the female subject's male partner is required. Subjects who utilize a hormonal contraceptive as one of their birth control methods must have used the same method for at least three months prior to study dosing. Hormonally-based contraceptives permitted for use in this protocol are as follows:

- Oral contraceptives (either combined or progesterone only)
- Injectable progesterone
- Implants of levonorgestrel
- Transdermal contraceptive patch
- Contraceptive vaginal ring

Not all of these methods may be approved in each of the countries where the study is being conducted: please refer to local product information. Additional local regulatory requirements may apply.

Female subjects must also refrain from egg donation and in vitro fertilization during treatment and until at least 90 days after the last dose of study drug.

3) Contraception Requirements for Male Subjects

It is theoretically possible that a relevant systemic concentration may be achieved in a female partner from exposure of the male subject's seminal fluid. Therefore, male subjects with female partners of childbearing potential must use condoms during treatment until 90 days after the last dose of study drug. Female partners of male study subjects are asked to select one of the above methods.

Male subjects must also refrain from sperm donation during treatment and until at least 90 days after the last dose of study drug.

4) Unacceptable Birth Control Methods

Birth control methods that are unacceptable include periodic abstinence (e.g., calendar, ovulation, symptothermal, post-ovulation methods), withdrawal (coitus interruptus), spermicides only, and lactational amenorrhea method (LAM). Female condom and male condom should not be used together.

5) Procedures to be Followed in the Event of Pregnancy

Subjects will be instructed to notify the investigator if they become pregnant at any time during the study, or if they become pregnant within 90 days of last study drug dose. Subjects who become pregnant or who suspect that they are pregnant during the study must report the information to the investigator and discontinue study drug immediately. Subjects whose partner has become pregnant or suspects she is pregnant during the study must report the information to the investigator. Instructions for reporting pregnancy, partner pregnancy, and pregnancy outcome are outlined in Section 6.21.5.2.

# **VERSION HISTORY**

Version	Version Date	Description
1.0	04 January 2021	Original signed version
1.1	26 January 2021	Adjust language for Liver Biopsy Evaluable Analysis Set
1.2	10 February 2021	Updated per Sponor request: Indicate two sets of biopsy data (local read v.s. central read); Added an analysis for ELF Week 12 data if available, and adjust analysis visit windown for Week 12 ELF; F4 Safety Set added for selected safety analysis
2.0	05 March 2021	Second signed version

# LIST OF ABBREVIATIONS

Abbreviation	Definition	
ADA	Anti-drug Antibodies	
AE	Adverse Event	
AESI	Adverse Event of Special Interest	
ALP	Alkaline Phosphatase	
ALT	Alanine Aminotransferase	
ANCOVA	Analysis of Covariance	
AST	Aspartate Aminotransferase	
ATC	Anatomical Therapeutic Chemical	
BLQ	Below Limit of Quantification	
BMI	Body Mass Index	
BSAP	Bone Specific Alkaline Phosphatase	
СЗМ	Neo-epitope of MMP-9 Mediated Degradation of Type III Collagen	
CLDQ-NAFLD	Chronic Liver Disease Questionnaire-Nonalcoholic Fatty Liver Disease	
CP	Child Pugh	
CRN	Clinical Research Network	
CRF	Case Report Form	
CSR	Clinical Study Report	
cT1	Corrected T1	
CTCAE	Common Terminology Criteria for Adverse Events	
DILI	Drug-Induced Liver Injury	
DMC	Data Monitoring Committee	
DXA	Dual Energy X-ray Absorptiometry	
eDISH	Evaluation of Drug-Induced Serious Hepatotoxicity	
ECG	Electrocardiogram	
EFX	Efruxifermin	
ELF™	Enhanced Liver Fibrosis Panel	
EOT	End of Treatment	
FAS	Full Analysis Set	
GGT	Gamma Glutamyl Transferase	
HRQoL	Health-Related Quality of Life	
INR	International Normalized Ratio	
LLOQ	Low Limit of Quantification	
MedDRA	Medical Dictionary for Regulatory Activities	
MELD	Model for End-Stage Liver Disease	
MMRM	Mixed-Model Repeated-Measures	
NAb	Neutralizing Antibody	
NAFLD	Nonalcoholic Fatty Liver Disease	
NAS	NAFLD Activity Score	
NASH	Nonalcoholic Steatohepatitis	
PK	Pharmacokinetics	
PPAS	Per Protocol Analysis Set	
SAE	Serious Adverse Évent	
SAP	Statistical Analysis Plan	
SF-36	Short Form 36 Health Survey	

Abbreviation	Definition
SOC	System Organ Class
ТВ	Total Bilirubin
TEAE	Treatment-Emergent Adverse Event
TESAE	Treatment-Emergent Serious Adverse Event
TFLs	Tables, Figures, and Listings
WHO	World Health Organization
WPAI	Work Productivity and Activity Impairment

### 1 INTRODUCTION

The purpose of this Statistical Analysis Plan (SAP) is to provide a description of the statistical methods to be implemented for the analysis of the Cohort C data from Akero Therapeutics, Inc. Protocol AK-US-001-0101. A separate SAP has been provided for the analysis of Main Study data from Akero Therapeutics, Inc. Protocol AK-US-001-0101. The SAP will be finalized prior to unblinding of the Cohort C database. Any deviations from the SAP after database unblinding will be documented in the final Clinical Study Report (CSR).

### 2 STUDY OVERVIEW

### 2.1 Study Objectives

### 2.1.1 Primary Objective

The primary objective of this study is:

 To assess the safety and tolerability of EFX in NASH subjects with compensated cirrhosis

### 2.1.2 Secondary Objectives

The secondary objectives of this study are:

- To evaluate the change from baseline in liver stiffness as evaluated by FibroScan® at Week 16
- To evaluate the change from baseline in non-invasive plasma (serum) fibrosis biomarkers including liver fibrosis by ELF™ Test score and pro-C3 levels

### 2.1.3 Exploratory Objectives

The exploratory objectives of this study are:

- Change from baseline in markers of liver injury and function including alanine aminotransferase (ALT), aspartate aminotransferase (AST), alkaline phosphatase (ALP), gamma glutamyl transferase (GGT), bilirubin, International Normalized Ratio (INR), albumin, Model for End-Stage Liver Disease (MELD) score, and Child Pugh (CP) score
- Change from baseline in body weight and waist-to-hip ratio
- Change from baseline in bone mineral density of the lumbar spine, femoral neck, and total hip as measured by Dual Energy X-ray Absorptiometry (DXA)
- The proportion of subjects whose fibrosis regresses by ≥ 1-stage according to the NASH CRN classification
- The proportion of subjects who had no worsening in NAS with improvement in fibrosis stage
- The proportion of subjects who had at least 2 points improvement in NAS with no worsening in fibrosis stage
- The proportion of subjects who had ≥ 1 point improvement in NAS, fibrosis, steatosis, lobular inflammation or hepatocellular ballooning

[figure not shown]
- Changes from baseline in health-related quality of life (HRQoL)
- Changes from baseline in lipoprotein profile and markers of lipid metabolism, insulin sensitivity and glycemic control
- Change from baseline in body fat distribution as measured by DXA total body composition
- Plasma concentrations of EFX
- To evaluate decompensated liver disease events including ascites, hepatic encephalopathy (HE), or variceal bleeding

### 2.2 Study Design

#### 2.2.1 Overview

This is a Phase 2a, randomized, double-blind, placebo-controlled study evaluating the safety and efficacy of EFX in subjects with NASH.

Cohort C will enroll approximately 30 subjects with biopsy-proven NASH. All subjects in Cohort C will have F4 fibrosis. Subjects meeting the study's entry criteria will be randomly assigned in a 1:2 ratio into 2 treatment groups as shown in the figure below:

There will be no stratification for Cohort C. Study drug will be administered subcutaneously once weekly (QW) for a total of 16 weeks. After 16 weeks of treatment, a safety follow-up visit will occur at Week 20. Following 16 weeks of treatment, subjects will be given the option to collect an end of treatment biopsy.

This study will be conducted at approximately 30 sites in the U.S. Additional sites may be added, depending on subject accrual rates.

### 2.2.2 Sample Size Determination

Since the primary objective is to assess the safety and tolerability of EFX in NASH subjects with compensated cirrhosis, the sample size is determined based on clinical considerations, and the treatment comparisons of efficacy measurements are not powered.

### 2.3 Study Endpoints

## 2.3.1 Secondary Efficacy Endpoints

### The secondary endpoints are:

- Change from baseline in liver stiffness as evaluated by FibroScan® at Week 16
- Changes from baseline in non-invasive biomarkers including Pro-C3 at Weeks 12, 16 and 20, and liver fibrosis by ELF™ Test score at Weeks 6, 12 and 16

### 2.3.2 Exploratory Efficacy Endpoints

### The exploratory endpoints are:

- Change from baseline in markers of liver injury and function including ALT, AST, ALP, GGT, bilirubin, INR, albumin, MELD score, and CP score at Weeks 12, 16 and 20
- Change from baseline in body weight and waist-to-hip ratio at Weeks 12, 16 and 20
- Change from baseline in bone mineral density of the lumbar spine, femoral neck, and total hip as measured by DXA at Week 16
- The proportion of subjects at Week 16 whose fibrosis regresses by ≥ 1-stage according to the NASH CRN classification
- The proportion of subjects at Week 16 who had no worsening in NAS with improvement in fibrosis stage
- The proportion of subjects at Week 16 who had at least 2 points improvement in NAS
- The proportion of subjects at Week 16 who had ≥ 1point improvement in NAS, fibrosis, steatosis lobular inflammation or hepatocellular ballooning
- The proportion of subjects at Week 16 who had NASH resolution (0-1 Point Inflammation, 0 Point Ballooning)
- The proportion of subjects at Week 16 who had fibrosis improvement ≥ 2-stage
- Changes from baseline in HRQoL (SF-36, CLDQ-NAFLD, WPAI) at Weeks 12 and 16
- Changes from baseline in lipoprotein profile and markers of lipid metabolism, insulin sensitivity and glycemic control at Weeks 12, 16 and 20
- Change from baseline in body fat distribution as measured by DXA total body composition at Week 16
- Plasma concentrations of EFX
- The incidence and severity of any decompensated liver disease events including ascites, hepatic encephalopathy (HE), or variceal bleeding
- Changes from baseline in Neo-epitope of MMP-9 Mediated Degradation of Type III Collagen (C3M)
- Changes from baseline in platelets at Weeks 12, 16 and 20
- Change from baseline in liver steatosis as evaluated by FibroScan® (CAP) at Week 16

### 2.3.3 Safety Endpoints

The safety endpoint is the safety and tolerability of EFX in NASH subjects with compensated cirrhosis.

Safety analyses include: summaries of extent of exposure, adverse events (AEs), laboratory evaluations, electrocardiogram (ECG), vital sign assessments, body weight, anti-drug antibody (ADA) and neutralizing antibody (NAb) assessments, and concomitant medication usage.

### 3 STATISTICAL METHODOLOGY

### 3.1 General Considerations

#### 3.1.1 Analysis Day

Analysis day will be calculated from the date of first dose of study drug. The day of the first dose of study drug will be Day 1, and the day immediately before Day 1 will be Day -1. There will be no Day 0, in alignment with international data standards for clinical trials. Analysis day will be calculated as (date of clinical event – date of first dose of study drug) + 1 if the date of the event is on or after the date of first dose and as (date of clinical event – date of first dose of study drug) if the date of event is before the date of first dose.

#### 3.1.2 Analysis Visits

Scheduled visits will be assigned to analysis visits as recorded on the Case Report Form (CRF). Unscheduled and early termination visits for ELF™ will be assigned to analysis visits according to the following visit windows:

Analysis Visit	Target Analysis Day	Low Analysis Day	High Analysis Day
Week 6	43	22	64
Week 12	85	65	99
Week 16	113	100	141
Note: if the unscheduled collection or early term collection is >21 days after the last dose			

Note: if the unscheduled collection or early term collection is >21 days after the last dose of study drug, it will not be used in analyses.

For ALT, markers of liver injury and function, waist-to-hip ratio, biomarkers, pro-C3 and HRQoL, unscheduled and early termination visits will be assigned to analysis visits according to the following visit windows:

Analysis Visit	Target Analysis Day	Low Analysis Day	High Analysis Day
Week 1	8	2	15
Week 4	29	16	43
Week 8	57	44	71
Week 12	85	72	99
Week 16	113	100	127
Week 20 Safety follow-up	141	128	EOS

Note: if the unscheduled collection or early term collection is >14 days after the last dose of study drug, it will not be used in analyses.

For body weight, unscheduled and early termination visits will be assigned to analysis visits according to the following visit windows:

Analysis Visit	Target Analysis Day	Low Analysis Day	High Analysis Day
Week 1	8	2	11
Week 2	15	12	18
Week 3	22	19	25
Week 4	29	26	32
Week 5	36	33	39
Week 6	43	40	46
Week 7	50	47	53
Week 8	57	54	60
Week 9	64	61	67
Week 10	71	68	74
Week 11	78	75	81
Week 12	85	82	88
Week 13	92	89	95
Week 14	99	96	102
Week 15	106	103	109
Week 16	113	110	127
Week 20 Safety	141	128	EOS
follow-up			

Note: if the unscheduled collection or early term collection is >14 days after the last dose of study drug, it will not be used in analyses.

The efficacy assessments from two FibroScan® (Screening and Week 16) and the safety assessments from two DXA Scans (Screening and Week 16) will be considered for the analysis regardless of when the second assessment or biopsy takes place. Unscheduled visits after the first dose of study drug and early termination visits will be assigned as post-baseline.

For PK concentration summaries, a concentration that is intended as predose will be excluded from analysis if it is >24 hours before a dose or after the current dose. Beyond this rule, PK concentrations must be within the visit window to be included in summary statistics of PK.

Within an analysis visit window, the measurement from the scheduled visits will be used if available. If no scheduled visit occurs, the measurement from the visit closest to the defined target analysis day within the window will be used. If there is more than one measurement with equal distance to the defined target analysis day, the latter will be used. If no visits occur within a visit window, the measurement for this visit will be treated as missing.

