- z The Safety Follow-up visit should be performed 4 weeks following the last dose of study drug. For subjects who complete the study, this will be Week 20. Subjects who terminate the study early should have this visit 4 weeks following the last dose of study drug received.
- aa Subjects will be given the option to collect an end of treatment biopsy. Biopsy should be taken within 2-4 weeks of last dose of EFX.

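### Early terminators' Week 20 Pro-C3 value in Cohort C is not a Week 20 measurement, and the 14-day exclusion contradicts the SAP's own Week 20 window

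*SAP*

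**What the plan says.** SAP 2.3.1 lists among the Cohort C secondary endpoints "Changes from baseline in non-invasive biomarkers including Pro-C3 at Weeks 12, 16 and 20". SAP 3.1.2 then sets three rules that bear on the Week 20 value.

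- Scheduled visits go by label: "Scheduled visits will be assigned to analysis visits as recorded on the Case Report Form (CRF". No day limit is attached.
- Day windows are given for other visits. For Pro-C3, biomarkers, ALT, liver markers, waist-to-hip ratio and HRQoL, "unscheduled and early termination visits will be assigned to analysis visits according to the following visit windows". The row "Week 20 Safety follow-up" has target Day 141, low Day 128 and high EOS. The body-weight table has the same row.
- Both tables carry the same exclusion: "if the unscheduled collection or early term collection is >14 days after the last dose of study drug, it will not be used in analyses".

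A later sentence in the section adds: "Within an analysis visit window, the measurement from the scheduled visits will be used if available". It is followed by a statement that a window with no visit is treated as missing.

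Protocol Appendix B has separate columns for ET and for the Week 20 Safety follow-up. Footnote z says of the latter that for completers it is Week 20, and: "Subjects who terminate the study early should have this visit 4 weeks following the last dose of study drug received". Protocol 3.4 gives the same 4-week timing. Appendix B marks dosing on Day 1 and Weeks 1 to 15, but not at Week 16.

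SAP 3.4.1.2 analyses ELF on the FAS with LOCF for missing values and repeats the analysis without imputation on the Biomarker Analysis Set and the PPAS. Pro-C3 is to be handled in a similar manner, including at Week 20.

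**The concern.** Week 20 is the only post-treatment time point for Pro-C3, so it is where a reader would look for persistence off drug. The rules can put into it, for a subject who stopped early, a value taken weeks or months before Day 141 after a short exposure. Alternatively they can fill it with a carried-forward value, which assumes the persistence that the visit is there to examine. The SAP does not say whether an early terminator's follow-up counts as a scheduled visit or as an early termination visit, so the programmer has to choose.

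The second problem is internal. The SAP provides a Week 20 row for unscheduled and early termination samples and then excludes essentially everything that could fall in it. If a scheduled Week 20 value is missing, a real off-drug sample from Day 128 onward would be discarded and an earlier value carried forward in its place.

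**Working it through.** **Inputs.** From SAP 3.1.2: window Day 128 to EOS, target Day 141, 14-day exclusion. From Protocol Appendix B: last marked dosing visit Week 15, visit tolerance ±3 days, follow-up at last dose + 28 days for early terminators. From Protocol 1.4.2.1: 6 of 69 subjects discontinued investigational product in Phase 1b. Cohort C size: about 30 (20 EFX, 10 placebo).

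**The SAP's own figures.** Target = 7 × 20 + 1 = 141. The midpoint of Weeks 16 and 20 is (113 + 141)/2 = 127, so the window opens on Day 128. Both reproduce.

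**14-day rule against the Week 20 row.** Last usable unscheduled or ET day = last dose + 14.

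| Last dose | Last usable day | Gap at Day 128 |
|---|---|---|
| Day 106 (Week 15) | 120 | 22 days: excluded |
| Day 109 (Week 15 + 3) | 123 | 19 days: excluded |
| Day 113 | 127 | 15 days: excluded |
| Day 114 | 128 | 14 days: allowed |

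The row can accept a sample only if the last dose is on Day 114 or later. That is 8 days past the planned last dose and outside the ±3-day tolerance.

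**Early terminators' follow-up.** Last dose at week k is Day 7k + 1, and follow-up is 28 days later.

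| Last dose | Follow-up | Days before 141 | Window by actual day |
|---|---|---|---|
| Day 1 | Day 29 | 112 | Week 4 |
| Week 3 (Day 22) | Day 50 | 91 | Week 8 |
| Week 8 (Day 57) | Day 85 | 56 | Week 12 |
| Week 14 (Day 99) | Day 127 | 14 | Week 16 |

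Of the 15 possible early last doses (Day 1 to Week 14), follow-up on the target day falls in the Week 4 window for 3, Week 8 for 4, Week 12 for 4, Week 16 for 4 and Week 20 for none. Last dose at Week 14 reaches Day 128 to 130 only by using the +3-day tolerance.

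**Three readings of SAP 3.1.2 for that visit.**

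1. Scheduled, by label: a Day 29 to 127 value is analysed as Week 20.
2. Scheduled, but windows bind: Week 20 is missing, and the FAS fills it by LOCF. The SAP does not say whether the follow-up value then counts at an earlier visit.
3. Early termination visit: 28 > 14, so it is dropped, and the FAS fills Week 20 by LOCF.

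On none of these is the FAS Week 20 value a Week 20 measurement.

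**Completers.** Day 141 ± 3 = Day 138 to 144, which is a true Week 20 value. It lies 141 − 106 = 35 days after the last planned dose (29 to 41 with tolerances), not the 28 that footnote z also states.

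**Number affected.** Cohort C dropout is not given. An assumed range of 0 to 20% means 0 to 6 of 30. The Phase 1b rate, 6/69 = 8.7%, gives 30 × 0.087 = 2.6, about 3. Each affected EFX subject is 1/20 = 5% of that arm.

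**The case against.** The strongest reply is that completers will supply most of the data, and their values are sound. The 14-day rule does not touch a scheduled Week 20 visit. The CRF is not among the documents, and the sentence on selection within a window can be read as windowing scheduled visits too, so entry by label at any day is an inference. Unscheduled Pro-C3 samples from Day 128 onward should be rare. Unimputed repeats on the Biomarker Analysis Set and the PPAS are already planned. The protocol defines the visit by time since last dose, so pooling on that scale is defensible for a question about persistence. Efficacy in Cohort C is not powered.

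All of this limits the size of the problem, but none of it removes the problem. The alternative reading leads to LOCF, not to a Week 20 value. The unimputed repeats are supporting analyses, and they do not settle how the visit is labelled.

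A reader might infer more than the documents support:

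- *That the Week 20 endpoint as a whole is mislabelled.* It is a mixture: only early terminators, and missing values filled by LOCF, are affected.
- *That the window can never accept a sample.* A last dose on Day 114 or later opens it. The SAP's exposure category above 16 weeks allows for a last dose on Day 113 or later.
- *That LOCF distorts every Week 20 marker.* SAP 3.4.2 analyses exploratory endpoints on observed values, with CAP as the exception. Only the label rule reaches them.
- *That the error favours EFX.* In Phase 1b four of the six discontinuations were at 140 mg QW. At 70 mg or below it was 1 of 37 on EFX (52 − 9 − 6 = 37) against 1 of 17 on placebo. Nor do the documents show how Pro-C3 behaves after stopping, so false persistence is a possibility and not a finding.

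**Conclusion.** The point holds in limited form. For completers, Week 20 Pro-C3 is measured at Week 20. For early terminators, the main FAS analysis uses either a value from about Day 29 to 127 under the Week 20 label or a carried-forward, usually on-treatment, value, and the SAP does not say which. Independently, the Week 20 row and the 14-day exclusion contradict each other for anyone dosed on schedule, in both the Pro-C3/biomarker table and the body-weight table.

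The effect is probably small: one time point of one secondary biomarker in an unpowered cohort of about 30, with about 3 subjects affected if the Phase 1b rate applied. That rate is an assumption, and no direction of bias or imbalance between arms is established. The rules should still be corrected, because as written they yield a wrong value and are not merely short of detail.

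**What to change.** In SAP 3.1.2 and 3.4.1.2:

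1. Exempt the Week 20 Safety follow-up row, in both tables, from the exclusion of samples taken more than 14 days after the last dose.
2. Do not carry on-treatment values by LOCF into Week 20. Make the observed-value analysis the main Week 20 Pro-C3 analysis.
3. State that a Safety Follow-up before Day 128 is not counted as Week 20 and is summarised separately as 4 weeks after last dose. A sensitivity analysis pooling by time since last dose is optional.

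The protocol's two timings for this visit, 4 weeks after the last dose and Week 20, also need to be reconciled with dosing marked through Week 15, which puts Week 20 five weeks after the last planned dose.

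The cost is a few sentences and a programming change. The Week 20 comparison would have slightly fewer subjects, mostly completers, and that selection should be acknowledged when it is reported. If the change comes after unblinding, SAP section 1 requires it to be documented in the CSR.
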